Pap Smear Collection With the Papette Brush: A Pragmatic Study

NCT05034614

5/20/2021

General Study Information

Principal Investigator: [name], PA-C, MS

Co-Investigators: [REDACTED]

Study Title: Pap smear collection with the Papette Brush: A Pragmatic Study

Protocol version number and date: Version 1; 5/20/2021

Research Question and Aims

Hypothesis: The Papette brush used for cervical cancer screening is non-inferior to traditional spatula and cytobrush in obtaining a satisfactory endocervical sample for cytology.

Aims, purpose, or objectives:

- 1) Compare use of Papette brush to traditional spatula and cytobrush for cervical cancer screening.
- 2) Analyze rate of “inadequate endocervical cells” reported in cytology samples obtained by using Papette and traditional spatula and cytobrush.
- 3) Evaluate operator experience with Papette vs. traditional spatula and cytobrush in terms of ease of usage, time of collection, procedure related cervical bleeding and perceived pain.

Background (*Include relevant experience, gaps in current knowledge, preliminary data, etc.*):

The Papette brush, in contrast to the spatula-cytobrush, is a single device used for Pap smear collection that obtains the exocervix and endocervix sample simultaneously. Despite being available since the early 90's and a report that indicated adequate sampling with decreased bleeding associated with Papette use (ref), this device has not been extensively studied. A Cochrane report published in 2000 showed superiority of combined spatula-cytobrush to just spatula for cervical cells sampling in Pap smear. Despite simplicity in design, the Papette has also not been widely used in our institution. One main driver is cost – the Papette costs at least twice the cytobrush-spatula kit. The Papette has been reported to obtain a satisfactory sample in 91.4% of women and may provide increased patient and provider satisfaction due to ease of use as well as potentially decreased post-procedure cervical bleeding. This study will compare the Papette to the spatula-cytobrush for Pap smear sample collection.

Reference:

P Martin-Hirsch ¹, G Jarvis, H Kitchener, R Lilford. Collection devices for obtaining cervical cytology samples: A Cochrane Database System Review. 2000; (2):CD001036.

Study Design and Methods

Methods: *Describe in lay terms, completely detailing the research activities that will be conducted by Mayo Clinic staff under this protocol.*

The Papette and spatula/cytology brush for cervical cancer screening are currently both available for use in the primary care clinics (Community Internal Medicine and Family Medicine) and Obstetrics and Gynecology clinic at Mayo Rochester campus. However, providers in Community Internal Medicine would like additional data on the benefits of one collection method versus the other. Although, both methods of Pap smear collection are available this is not typically documented in the chart so a simple chart review study can not address the outcome.

Within Community Internal Medicine (CIM) we aim to complete 353 Pap smears using the Papette and 353 Pap smears using the traditional spatula/cytology brush from July 2021-June 2022. The total sample size will be 706 patients. Cluster sampling will be used: CIM practice in Rochester are located at Baldwin, NW, NE and SE clinics. The Baldwin practice is divided into 4 care teams: Ba5A, Ba5B, Ba6A and Ba6B. The Papette brush will be used to obtain Pap smear samples in women seen at CIM Ba5A, Ba5B and NW clinic while spatula/cytobrush will be used to obtain Pap smear samples at Ba6A, Ba6B, NE and SE clinics. Collection will be done until end of study date or until target sample size is met whichever comes first.

Outcome data to be collected:

-Demographics

-Cytology report on cellular adequacy: a retrospective review of subject medical record will be done to capture cytology report on completed Pap smear exam.

-Cervical bleeding with collection, ease of usage, time of collection, perceived pain, indication for pap smear, problem encountered: Provider who performed pap smear will be asked to complete a short questionnaire right after completion of exam.

Data will be stored in a secure database with only research members listed on the IRB having access to data.

Subject Information

Target accrual is the proposed total number of subjects to be included in this study at Mayo Clinic. A "Subject" may include medical records, images, or specimens generated at Mayo Clinic and/or received from external sources.

Target accrual: 706 Pap smear samples

Subject population (children, adults, groups): Adult women aged 21-64 years old eligible for pap smear exam; Providers performing Pap smear samples in CIM.

Inclusion Criteria: Adult women aged 21-64 years old who gave consent for medical records to be accessed and who will have a Pap smear exam in CIM from July 2021 through June 2022; Providers performing Pap smear samples in CIM.

Exclusion Criteria: Women <21 or >64; has vaginal spotting present during cervical sampling; did not give consent to have medical records accessed; Providers not part of CIM.

Biospecimens

Collection of blood samples. When multiple groups are involved copy and paste the appropriate section below for example repeat section b when drawing blood from children and adults with cancer.

a. **From healthy, non-pregnant, adult subjects who weigh at least 110 pounds.** For a minimal risk application, the amount of blood drawn from these subjects may not exceed 550ml in an 8 week period and collection may not occur more frequently than 2 times per week.

Volume per blood draw: N/A ml

Frequency of blood draw (e.g. single draw, time(s) per week, per year, etc.) N/A

b. **From other adults and children considering age, weight, and health of subject.** For a minimal risk application, the amount of blood drawn from these subjects may not exceed the lesser of 50 ml or 3 ml per kg in an 8 week period, and collection may not occur more frequently than 2 times per week.

Volume per blood draw: N/A ml

Frequency of blood draw (e.g. single draw, time(s) per week, per year, etc.) N/A

Prospective collection of biological specimens other than blood: Pap smear sample

Review of medical records, images, specimens

Check all that apply (data includes medical records, images, specimens).

Only data that exists before the IRB submission date will be collected.

Date Range for Specimens and/or Review of Medical Records:

Examples: *01/01/1999 through 12/31/2015*, or all records through *mm/dd/yyyy*.

Note: The Date Range must include the period for collection of baseline data, as well as follow-up data, if applicable.

The study involves data that exist at the time of IRB submission **and** data that will be generated after IRB submission. Include this activity in the Methods section.

Examples

- The study plans to conduct a retrospective chart review and ask subjects to complete a questionnaire.
- The study plans to include subjects previously diagnosed with a specific disease and add newly diagnosed subjects in the future.

The study will use data that have been collected under another IRB protocol. Include in the Methods section and enter the IRB number from which the research material will be obtained. *When appropriate, note when subjects have provided consent for future use of their data and/or specimens as described in this protocol.*

Enter one IRB number per line, add more lines as needed

Data Specimens Data & Specimens _____

Data Specimens Data & Specimens _____

Data Specimens Data & Specimens _____

Data Analysis

Power analyses may not be appropriate if this is a feasibility or pilot study, but end-point analysis plans are always appropriate even if only exploratory. Provide all information requested below or provide justification if not including all of the information.

Power Statement:

A total sample size of 706 women (353 per cluster) is needed to detect a difference of 0.2 between the means of the brushes with 80% power, a two-sided significance level of 0.05, and an intraclass correlation was 0.1.

Data Analysis Plan:

Descriptive statistics will be reported for patient demographics by type of procedure. Chi-square tests will be used for categorical variables and Kruskal-Wallis test for continuous variables. For the primary analysis, a linear mixed model will be used to model the impact of procedure type on the rate of inadequate endocervical cells. The model will include a fixed procedure effect and a random cluster effect. As a sensitivity analysis, covariates such as age, previous bleeding history, and other factors will be adjusted for in the mixed model. The secondary outcome will be categorized as binary variable for whether the patient experienced procedure related bleeding. A logistic mixed model will be utilized to analyze any difference in bleeding between procedure types adjusting for the same variables as the primary analysis. Questionnaires filled out by the provider will be compared by procedure type to evaluate ease of use and other measures from a provider standpoint.

Endpoints:

Primary: Analyze rate of “inadequate endocervical cells” reported in cytology samples obtained by using Papette and traditional spatula and cytobrush.

Secondary: Evaluate procedure related bleeding experienced by using the Papette and traditional spatula and cytobrush.

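### The only stated hypothesis is non-inferiority, but the plan gives no margin and no decision rule, so as written it can be confirmed only by a significant Papette advantage

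*Combined protocol and SAP*

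**What the plan says.** Under Research Question and Aims, the protocol states one hypothesis: "The Papette brush used for cervical cancer screening is non-inferior to traditional spatula and cytobrush in obtaining a satisfactory endocervical sample for cytology". Aim 1 is neutral: "Compare use of Papette brush to traditional spatula and cytobrush for cervical cancer screening". Aim 2 and the primary endpoint concern the rate of inadequate endocervical cells "reported in cytology samples obtained by using Papette and traditional spatula and cytobrush".

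Under Data Analysis, the Power Statement says that 706 women, 353 per group, are "needed to detect a difference of 0.2 between the means of the brushes with 80% power, a two-sided significance level of 0.05", with an intraclass correlation of 0.1. It does not give the scale of the 0.2. The Data Analysis Plan describes its main model in these words: "a linear mixed model will be used to model the impact of procedure type on the rate of inadequate endocervical cells". Procedure enters as a fixed effect and cluster as a random one. The Data Analysis Plan states no test, significance level, margin or confidence-limit rule for this model, and neither it, the Power Statement nor the Endpoints mentions non-inferiority.

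The Background offers one reference rate: "The Papette has been reported to obtain a satisfactory sample in 91.4% of women". No rate is given for spatula/cytobrush, and the document does not say that 91.4% is the complement of the primary endpoint.

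**The concern.** A non-inferiority claim needs a margin fixed in advance and a rule that sets a confidence limit against it. Without them, possible results fall into three groups.

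- **Papette significantly better.** Non-inferiority follows for any margin.
- **No significant difference.** This does not show non-inferiority, because the interval may still include a deficit that matters.
- **Papette significantly worse.** The plan can say that it is worse, but not whether the deficit exceeds what is tolerable.

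Only the first group confirms the hypothesis, and the hypothesis does not require an advantage. In the other two the conclusion depends on a margin that someone would have to choose after the data are known. The same data could then be reported as supporting or not supporting the claim.

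**Working it through.** **1. Does the sample size reveal an intended margin?** Inputs from the Power Statement: difference 0.2, two-sided 0.05 (z = 1.960), 80% power (z = 0.842), ICC 0.1. Reading 0.2 as a standardised difference (SD = 1, assumed):

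2 × ((1.960 + 0.842)/0.2)² = 392.4 per group; 392.4 × 0.9 = 353.2 per group, 706 in total.

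This matches the stated figure. The factor 0.9 is inferred as 1 minus the ICC. A non-inferiority test with a margin of 0.2 SD, true difference 0 and one-sided 0.025 gives the same number, so the sample size does not settle what was intended.

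**2. Could 0.2 serve as the margin?** On the raw scale it is 20 percentage points. In SD units it is 0.2 × √(p(1−p)), which is 2.8, 5.6 or 8.0 points at assumed inadequate rates p of 2%, 8.6% or 20%. These are very different margins.

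**3. Chance of confirming the hypothesis when the devices are equal.** A valid two-sided 0.05 test finds the Papette significantly better 2.5% of the time. In the other 97.5% the plan gives no confirmation.

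**4. How far the reading of one result depends on the margin.** Assumed observed inadequate rates are 11.6% (Papette) and 8.6% (spatula/cytobrush), 353 per group. The 8.6% borrows 100 − 91.4 for the comparator purely as an illustration.

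- Independent samples: SE = √(0.116 × 0.884/353 + 0.086 × 0.914/353) = 0.02265. The difference is 3.0 points, 95% CI 3.0 ± 1.96 × 2.265 = -1.4 to 7.4, p = 0.19. It fails a 5-point margin and passes a 10-point one.
- ICC 0.1: the Methods list seven units, each using one device (three Papette, four spatula/cytobrush). With seven equal units, 706/7 = 100.9 women each, the design effect is 1 + 99.9 × 0.1 = 10.99. The SE becomes 0.02265 × √10.99 = 0.0751 and the 95% CI is -11.7 to 17.7. It fails both margins.

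The same 3.0-point deficit at other assumed rates:

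| Inadequate, Papette vs comparator | 95% CI, independent | 95% CI, ICC 0.1 |
|---|---|---|
| 8.6% vs 5.6% | -0.8 to 6.8 | -9.5 to 15.5 |
| 5% vs 2% | 0.3 to 5.7 | -6.0 to 12.0 |
| 23% vs 20% | -3.1 to 9.1 | -17.1 to 23.1 |

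With independent samples every row fails 5 points and passes 10. At ICC 0.1 no row passes 10, and the 5% versus 2% result is no longer significant.

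**5. Power of 353 per group for a non-inferiority test.** Equal true rates p in both groups, SE = √(2p(1−p)/353), multiplied by √10.99 for clustering. Power = Φ(M/SE − 1.96) at M = 5 points; the margin giving 80% power is 2.80 × SE.

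| p | SE, independent | Power at 5 points | Margin for 80% | SE, ICC 0.1 | Power at 5 points | Margin for 80% |
|---|---|---|---|---|---|---|
| 2% | 0.0105 | over 99% | 3.0 | 0.0349 | 30% | 9.8 |
| 8.6% | 0.0211 | 66% | 5.9 | 0.0699 | 11% | 19.6 |
| 20% | 0.0301 | 38% | 8.4 | 0.0998 | 7% | 28.0 |

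These use normal quantiles. With seven clusters and two groups, a t quantile on 5 degrees of freedom (2.571 instead of 1.960) would widen every clustered interval further.

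**The case against.** The strongest reply is that a two-sided 0.05 level is compatible with non-inferiority: a two-sided 95% CI from the planned model could be set against a margin. That is correct. The fault lies in the missing margin and rule, and the two-sided level is not itself an error.

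Four stronger readings are tempting, and the documents do not support them.

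- A reader might infer that the analysis plan prescribes a two-sided test of difference. The two-sided level appears only in the Power Statement; the Data Analysis Plan names a model and leaves the test open. The Power Statement's wording does lean towards a difference test.
- A reader might infer that 706 can only be a superiority calculation. Step 1 of the working shows that it fits a 0.2 SD margin equally well.
- A reader might infer that the aims contradict the hypothesis. A non-inferiority study is also a comparison, so neutral aims are consistent with it.
- A reader might infer that the sponsor will report a non-significant difference as non-inferiority. The plan does not say so. It is silent on how such a result will be read.

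The converse reading, that 0.2 is already the margin, also fails: the text calls it a difference to detect and gives no scale.

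It is also fair to object that the rates, the 3-point deficit and the 5- and 10-point margins are not in the protocol. They are assumptions, used only to show that the conclusion turns on a number the plan does not give.

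**Conclusion.** The concern stands as a missing margin and decision rule for the protocol's only hypothesis. This is more than a missing detail, because the framework that is stated does not answer the question the study asks. That conclusion rests on the text alone and needs none of the assumed rates.

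The size of the problem does depend on assumptions. With independent samples, 353 per group could support margins of roughly 3 to 8 points at 80% power. At the plan's own ICC of 0.1 with seven equal units, the range is roughly 10 to 28 points before any t correction. Splitting 353 over three and four units instead gives design effects of 12.7 and 9.7, averaging 11.2, which changes little. Independent-sample figures alone would suggest that a 10-point margin is comfortably within reach; the stated ICC does not bear that out.

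**What to change.** Before outcome data are reviewed, take one of two routes.

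(a) Add to the Data Analysis Plan: 'Non-inferiority is declared only if the upper limit of the two-sided 95% CI for the risk difference in inadequate endocervical cells (Papette minus spatula/cytobrush) is below M percentage points. The interval comes from the linear mixed model fitted to a 0/1 outcome per sample, with a small-sample correction for three versus four clusters.' Fix and justify M, say whether 0.2 is that margin and on what scale, and restate the power of 706 for this test.

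(b) If no margin can be justified, or the restated power is too low, reword the hypothesis as a comparison of the two devices and state that a non-significant difference will not be read as non-inferiority.

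Either route is a text change and requires no new data items. Route (a) will expose low power for a tight margin if clustering is as strong as the plan assumes, and reaching 80% would then need a different design. Route (b) gives up the non-inferiority claim and is the realistic choice if the ICC is near 0.1.

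### The spotting exclusion is timed to the same moment as the bleeding outcome and should be re-timed to before device contact

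*Combined protocol and SAP*

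**What the plan says.** Among the exclusion criteria (Subject Information), a woman is not eligible if she "has vaginal spotting present during cervical sampling".

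The list of outcome data in the Methods section includes "Cervical bleeding with collection, ease of usage, time of collection, perceived pain". On who records these items and when, it says: "Provider who performed pap smear will be asked to complete a short questionnaire right after completion of exam".

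The device is fixed by care team or clinic: "The Papette brush will be used to obtain Pap smear samples in women seen at CIM Ba5A, Ba5B and NW clinic", with the spatula and cytobrush used at the other four sites. The provider therefore knows which device is in use.

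Under Endpoints, the one secondary endpoint is "Evaluate procedure related bleeding experienced by using the Papette and traditional spatula and cytobrush". The Data Analysis Plan makes it binary and adds: "A logistic mixed model will be utilized to analyze any difference in bleeding between procedure types". The third aim calls it "procedure related cervical bleeding and perceived pain", and the Background gives "potentially decreased post-procedure cervical bleeding" as a possible advantage of the Papette.

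The plan does not say who applies the spotting criterion, whether it is judged before the device touches the cervix, or how spotting is told apart from bleeding caused by the procedure.

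**The concern.** An eligibility criterion should be settled before the exposure can act on it. This one is timed to the sampling itself, which is when the device can cause bleeding. Read literally, blood that first appears while the device is in use satisfies both the exclusion and the secondary outcome. A woman could then leave the study because she had the event being counted.

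At stake is the comparison of bleeding between devices. If such exclusions were made more readily with one device than the other, the odds ratio from the logistic mixed model would be distorted. Judgements at the exam are made with the device known, and the protocol already states an expectation about bleeding.

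**Working it through.** **1. The two rules side by side**

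| | Exclusion | Outcome |
|---|---|---|
| Timing | during sampling | with collection |
| Site named | vaginal | cervical |
| Cause named | none | procedure related (aims, endpoints) |
| Judged by | not stated | provider who took the sample |
| Recorded | not stated | right after the exam |

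The timing coincides. The labels for site and cause differ and point to pre-existing spotting as the intent, but they are not an operating rule.

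**2. Inputs.** The plan gives no bleeding rate and no exclusion share, so it has no figure of its own to reproduce on this point. The bleeding rate b and the share f of device-caused bleeders who are excluded are assumptions. From the Power Statement I take only 353 women per group and the intraclass correlation of 0.1. From Methods I take 3 Papette and 4 spatula/cytobrush clusters.

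**3. Formula.** Removing a share f of bleeders and no non-bleeders changes the odds from b/(1 − b) to b(1 − f)/(1 − b), so the odds are multiplied by (1 − f). Hence

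observed OR = true OR × (1 − fP)/(1 − fC)

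observed rate = b(1 − f)/(1 − bf).

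If f is constant within an arm, the factor applies in every cluster, so it carries over to the odds ratio of the mixed model.

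**4. Results**

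- *Intended reading:* fP = fC = 0, the factor is 1, and there is no bias.
- *Literal reading, unequal shares, true OR 1.00:*
  - 30%/20%: 0.70/0.80 = 0.875; reversed, 0.80/0.70 = 1.14.
  - 10%/0%: 0.90; reversed, 1/0.90 = 1.11.
  - At b = 15% in both arms, 30%/20% gives observed rates of 0.105/0.955 = 11.0% and 0.120/0.970 = 12.4%.
- *Literal reading, equal shares:* true rates of 10% vs 20% become 0.08/0.98 = 8.2% vs 0.16/0.96 = 16.7% at f = 20%. The risk difference falls from 10 to 8.5 points. The OR is (0.10/0.90)/(0.20/0.80) = 0.44 before and after.

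**5. Size against precision** (b = 15%, shares 30%/20%, equal cluster sizes, ICC 0.1 assumed to apply to bleeding)

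- Design effects: 1 + (353/3 − 1) × 0.1 = 12.67 and 1 + (353/4 − 1) × 0.1 = 9.72.
- Variance of log OR: 12.67/(353 × 0.110 × 0.890) + 9.72/(353 × 0.124 × 0.876) ≈ 0.367 + 0.254 = 0.621, so SE ≈ 0.788.
- 95% interval: the OR multiplied or divided by exp(1.96 × 0.788) ≈ 4.7.
- Rejection rate under a true null: the shift is |ln 0.875|/0.788 = 0.134/0.788 ≈ 0.17 standard errors, giving about 5.3% against a nominal 5%.

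**6. What a count by arm would show.** To reach 353 analysed women, the exclusions needed are 353/(1 − bf) − 353. At b = 15% this is 353/0.955 − 353 ≈ 17 at f = 30% and 353/0.970 − 353 ≈ 11 at f = 20%.

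**The case against.** The strongest reply is that the criterion plainly means spotting the woman arrives with. It describes a state, it sits among eligibility rules, and the outcome is always named differently. Applied literally and consistently, it would remove every bleeder and leave the secondary endpoint empty, which cannot be intended. Bias also needs a chain the documents do not establish: the criterion is applied after device contact, cervical bleeding is treated as vaginal spotting, and this happens at different rates by device. The documents do not say who applies the criterion; that it would be the provider at the exam is an inference. All shares and rates are assumed, and a move to 0.875 is small beside an interval factor of about 4.7.

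Most of this stands, and it limits the point to the timing words. It does not answer the point, because seven care teams and clinics must apply the criterion and nothing written tells them to judge it before device contact. Nor does the planned adjustment for previous bleeding history help: covariates cannot restore women who were left out.

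A reader might infer that the problem could never be detected or repaired. The documents do not support that. The questionnaire itself is not shown, so a pre-sampling item cannot be ruled out, and the field for problems encountered might capture some cases. It is fair to say only that no pre-device record and no count of exclusions by arm is described.

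**Conclusion.** The timing of the exclusion overlaps the timing of the secondary outcome and should be corrected. Pre-existing spotting is the likelier intent, and on that reading there is no bias by this route. On the literal reading, the odds ratio is distorted only if the excluded share differs by device. The illustration of 0.875 or 1.14 rests on assumed shares of 30% and 20%. With equal shares, only the rates and the risk difference shrink.

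Three stronger conclusions might be drawn, and the documents support none of them:

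- *That the plan deliberately excludes outcome events.* The differing labels point the other way.
- *That the bias would favour the Papette.* An expectation of less bleeding is stated, but nothing shows how exclusions would fall, so the direction is unknown.
- *That the test would be seriously inflated, or the primary endpoint affected.* At 30%/20% and 15% bleeding the false-positive rate is about 5.3%, so the main harm would be a biased estimate. No effect on the rate of inadequate endocervical cells is claimed.

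This is a change that should be made to protect a secondary endpoint. It does not undermine the trial.

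**What to change.** 1. Re-time the exclusion to vaginal spotting present before any sampling device touches the cervix, without otherwise widening it. Extending it to cervical bleeding would change who is eligible.
2. State that bleeding first seen after device contact is an outcome and never a reason for exclusion.
3. Add one yes/no item on pre-device spotting, noted before sampling.
4. Report the number of women excluded for this reason by arm.

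The cost is a sentence or two in the protocol, one item and one count per arm. The real burden is a small workflow step: the item is noted before sampling, whereas the questionnaire is now completed after the exam, and it must also be kept for women who are then excluded. No extra patients or visits are needed.

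### The stated 80% power for 706 women at ICC 0.1 does not fit a design in which seven whole teams or clinics each use one brush

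*Combined protocol and SAP*

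**What the plan says.** The Power Statement (Data Analysis) reads: "A total sample size of 706 women (353 per cluster) is needed to detect a difference of 0.2 between the means of the brushes", continuing "with 80% power, a two-sided significance level of 0.05, and an intraclass correlation was 0.1". It gives no SD, event rate, number of clusters or cluster size, and names no formula.

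The Methods (Study Design and Methods) describe the clusters: "Cluster sampling will be used: CIM practice in Rochester are located at Baldwin, NW, NE and SE clinics". They add: "The Baldwin practice is divided into 4 care teams: Ba5A, Ba5B, Ba6A and Ba6B". Each unit uses one brush only. For the first arm, "The Papette brush will be used to obtain Pap smear samples in women seen at CIM Ba5A, Ba5B and NW clinic"; Ba6A, Ba6B, NE and SE use spatula/cytobrush. The target is per brush: "we aim to complete 353 Pap smears using the Papette and 353 Pap smears using the traditional spatula/cytology brush".

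Under the Data Analysis Plan, "a linear mixed model will be used to model the impact of procedure type on the rate of inadequate endocervical cells". It adds: "The model will include a fixed procedure effect and a random cluster effect".

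**The concern.** When whole teams or clinics are given one brush, differences between units are mixed with the difference between brushes. A positive ICC then inflates the variance of the comparison, by a factor of about 11 at roughly 101 women per unit and ICC 0.1. Yet 706 is fewer than the 785 or so women needed for a 0.2 SD difference with no clustering at all. The number looks as if the ICC had been used to lower the requirement.

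The wording of 353 per cluster adds to the doubt. The Methods list seven units and give 353 per brush, so 353 appears to be the size of an arm.

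The Power Statement is the plan's only justification for 706 women, and the hypothesis is one of non-inferiority. If true power is far below 80%, a finding of no difference is likely, or at least easily obtained, even when the brushes do differ. Readers could then mistake it for evidence that they perform alike.

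**Working it through.** **Inputs from the documents.** 353 women per brush; difference 0.2; two-sided 5%; 80% power; ICC 0.1; 3 Papette units and 4 spatula/cytobrush units.

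**Assumptions made here.** The cluster is the care team or clinic. Cluster sizes are equal within arm (353/3 = 117.67 and 353/4 = 88.25). The t figures use 7 − 2 = 5 df. The scale of 0.2 is not stated, so both readings are tried.

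**Step 1: reproduce 706.** With SD = 1, the unclustered need per arm is 2(1.960 + 0.842)²/0.2² = 392.4, or 784.9 in total. Then 784.9 × (1 − 0.1) = 706.4, or 353 per arm. Power with variance 2(0.9)/353 is 79.98%, which matches the plan. The factor (1 − ICC) applies when both brushes are used within each cluster, so that the cluster effect cancels. With no clustering, 706 women give 75.7%.

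**Step 2: reading A, 0.2 in SD units, allocation as in the Methods.**

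SE² = (0.1 + 0.9/117.67)/3 + (0.1 + 0.9/88.25)/4 = 0.0359 + 0.0275 = 0.0634, so SE = 0.2519 and 0.2/SE = 0.794.

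| ICC | Power, normal | Power, t (5 df) |
|---|---|---|
| 0.1 | 12% | 10% |
| 0.05 | 19% | 14% |
| 0.01 | 46% | 33% |
| 0 | 76% | 57% |

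Unlimited women in the same seven units at ICC 0.1 give only 13.1% (normal) or 10.5% (t). The limit is the number of units.

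**Step 3: reading B, 0.2 as 20 percentage points.** This is plausible because the endpoint is a rate in a linear model. With P for Papette and S for spatula/cytobrush:

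SE² = pP(1 − pP)[1 + 116.67 × ICC]/353 + pS(1 − pS)[1 + 87.25 × ICC]/353.

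At ICC 0.1 the bracketed factors are 12.67 and 9.725. The rates are assumed, since the Power Statement gives none.

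| Rates | Papette higher, normal / t | Spatula/cytobrush higher, normal / t |
|---|---|---|
| 5% v 25% | 60.7% / 43.9% | 67.5% / 49.5% |
| 10% v 30% | 51.5% / 36.8% | 55.8% / 40.0% |
| 20% v 40% | 41.8% / 29.7% | 43.6% / 31.0% |
| 30% v 50% | 37.7% / 26.9% | 38.4% / 27.4% |
| 40% v 60% | 36.7% / 26.2% | 36.7% / 26.2% |

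The only rate in the documents is the 91.4% satisfactory in the Background. Its complement, 8.6%, is a related but not identical measure. Taken as the Papette rate with spatula/cytobrush 20 points higher, it gives 59% (normal) or 42% (t).

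**Step 4: could a design effect give 706 on reading B?** Unclustered totals run from 92 (5% v 25%) to 188 (40% v 60%). Reaching 706 needs a design effect of 7.66 down to 3.75. At ICC 0.1 that is about 68 down to 28 women per cluster, or about 10 to 25 clusters, which the plan does not state. At 706/7 = 100.9 per cluster the design effect is 1 + 99.9 × 0.1 = 10.99, and the need is 1,013 to 2,069 women before any small-sample correction.

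**Step 5: interval widths at ICC 0.1.** On reading A, 1.960 × 0.2519 = ±0.49 SD (normal) and 2.571 × 0.2519 = ±0.65 SD (t). On reading B, with arms 20 points apart, about ±16–24 points (normal) or ±21–32 points (t).

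**The case against.** **The cluster is not defined.** Providers are also listed as subjects. If they were the only clusters, with no correlation at team level, 28 of them (equal arms, ICC 0.1, t) would give 81–98% on reading B. But the plan gives no provider count and assigns the brush by team or clinic, so correlation at that level cannot be assumed away. On reading A, 14 to 40 providers give only 17–36%. If the clusters were the four sites, with no variation between Baldwin teams, power for 0.2 SD is still only about 59% (normal). What stands is that the seven-unit reading, though natural from the Methods, is an inference.

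**The true ICC could be lower.** On reading B, 80% would be reached at an ICC below about 0.03–0.07 (normal) or 0.014–0.042 (t), depending on the rate. The plan itself specifies 0.1, however, and on reading A no ICC reaches 80%.

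**0.2 might be a non-inferiority margin with equal true rates.** The seven-unit formula would then give 81% (normal) or 62% (t) at a rate of 8.6%, 95% or 83% at 5%, and 51% or 36% at 20%. This conflicts with a Power Statement that is two-sided, speaks of detecting a difference and names no margin.

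**The reading B figures are not exact.** The rates are assumed, and a pooled t-test on 3 versus 4 cluster means is unreliable when the arm variances differ. A beta-binomial simulation of that test gave 27–54%, against 26–50% from the formula, and at 5% v 25% it reversed which direction had more power. The individual percentages are therefore approximate, but the shortfall remains.

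**Conclusion.** The point holds: the Power Statement is wrong as written. With seven teams or clinics as clusters, 353 women per arm and the plan's own ICC of 0.1, a true difference of 0.2 SD would be missed about 9 times in 10. A true difference of 20 points would be missed about 1 time in 3 to 3 times in 4, for lower-arm rates of 5–40%. The almost exact match of 785 × 0.9 to 706 favours the SD reading, although the plan names no formula.

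One exception on reading B should be recorded. At ICC 0.1 the normal figure passes 80% if the Papette rate is below about 1.3% and the spatula/cytobrush rate is 20 points higher. The 5-df figure does not pass 80% even there (at most 68%). Unequal cluster sizes (CV about 0.4–0.7) change little: 12%/10% on reading A and 36–67%/25–49% on reading B.

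Confidence is high that the stated 80% is not delivered under the allocation in the Methods. It is moderate on the size of the shortfall, which depends on the scale of 0.2.

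**What to change.** Rewrite the Power Statement:

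1. Delete the 80% claim and describe 353 as per arm.
2. State whether 0.2 is in SD units or percentage points, with the SD or the assumed inadequate rates and their source.
3. Define the cluster in both the Power Statement and the mixed model. The brush is assigned by care team or clinic, so that level has to be represented.
4. Restate power, or the detectable difference, for 353 per arm in 3 versus 4 clusters, with a between-cluster design effect and small-sample degrees of freedom. If 0.2 is in SD units, the reading A table supplies the figures. If it is percentage points, use the reading B formula with rates the sponsor can source.

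This costs one paragraph and no extra women. The price is a much less favourable stated power, which shows that the present allocation is underpowered at ICC 0.1.

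As an option for the sponsor to weigh, on the SD reading 706 women do give 80% if both brushes are used inside each team or clinic. That is a design change: every unit would have to use and record both devices. Neither step supplies a margin for the non-inferiority hypothesis, which remains a separate gap.
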